4.5 MEP Measurements

At CHOP, 30 of approximately 90 participants will be included for muscle phenotyping assessment as part of the study's aim to define the progression of physiological dysfunction in affected tissues. All participants will be offered the opportunity to participate, but 30 children will be selected on a first-come basis and must meet inclusion criteria. MEPs are measured using transcranial magnetic stimulation (TMS), a device which produces a momentary electromagnetic pulse which stimulates the motor cortex of the brain. We will use a Magstim 200² machine with a 70 mm figure-of-eight coil (Magstim Co, Wales, UK). Motor evoked potentials will be obtained from adhesive surface electrodes placed on the first dorsal interosseous (FDI) of the dominant hand, and recorded using an amplifier (CED 1902 isolated amplifier, CED, Cambridge UK), an analog-to-digital converter (CED 1401), and Signal 3.13 for Windows software (CED, Cambridge, UK). In the unlikely event that a

participant is ambidextrous, the right side will be measured. The TMS machine emits a low volume click with each stimulus; for safety considerations (see below) each subject will wear foam earplugs during the session.

Resting motor threshold (RMT) will be measured as the minimum stimulus intensity needed to elicit MEPs of at least 50uV in 5 of 10 trials. The optimal site of stimulation for the FDI muscle will be determined as the site with the lowest RMT for eliciting MEPs. Finding the RMT and optimal site will take approximately 20-30 single stimuli. Stimulation will consist of 20 stimuli, each separated by at least 4 seconds, at a pulse intensity of 110% MT, with the option to deliver up to 30 additional stimuli if more than half of the trials are affected by movement. No sessions will exceed 1800 pulses of TMS, a safety standard we have specified in prior studies at CHOP (IRB 12-009124) and by the stimulation lab at the University of Pennsylvania (Penn IRB #806532). The expected time for MEP recording, including set up time is 60 minutes.

The procedure detailed above has been included on other IRB approved studies at CHOP, including an open study by principle-investigator [name] (IRB 14-011627).

Useful References for Observational and Descriptive Research:

A copy of a recent publication describing the validation of these measures has been included.

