4.7 Primary and Secondary Endpoints

The primary goal of this study is to gather long-term serial quantitative clinical data using the measures validated during the three years of the study.

Aims 1: The primary endpoint (s) are the change in each of the clinical measures over time. The rate of change of each of these will be compared for responsiveness to change (SD of change/mean change).

Aim 2: Biochemical measures: The rate of change of frataxin and each platelet biomarker will be determined as primary endpoints. The rate of change over time will be determined to define which measures are most sensitive to disease progression.

Aim 3: Anatomical measures: The primary endpoints are the post exercise recovery time, Tau, for CrCest and the MEP size for MEP testing. The rate of change over time will be determined to define which measures are most sensitive to disease progression.

The secondary analyses are:

The rate of change of each measure the (neurological measures, biochemical measures and anatomic measures) as a function of age, GAA repeat length and sex, as determined by linear regression models

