Aim 2: Results will be summarized with standard descriptive statistics using parametric or non-parametric methods, as appropriate given the variable distributions. In this biochemical aim, the major analysis will examine the relationship of frataxin levels and downstream biomarkers with disease progression. This will be performed in 2 ways. First using cross sectional data, we will construct mixed linear models that allow the assessment of their relationship of marker values (frataxin, 13C metabolite levels, Apo A1) to age, GAA repeat length and sex. Secondly, we will assess the change in values over time both in absolute value and percent change to understand the overall meaning of results. In addition, the change over time will be examined in relation to age, sex, and GAA repeat length in linear models. We will also examine the levels of each marker at baseline with the change in clinical measures from aim 1. This will allow us to understand the degree to which clinical change reflects individual biochemical events and whether clinical and biochemical events correlate temporally. This analysis will be supplemented by analysis assessing whether the change in levels of the biomarkers predicts clinical change.

Aim 3. Each of the measures here (MEP, CrCEST) has differentiated FRDA subjects from controls in previous studies. For this proposal though, the crucial analyses should ascertain the relationship between physiological values from CrCEST and MEP and disease status from clinical measures. Results will be summarized with standard descriptive statistics using parametric or non-parametric methods, as appropriate given the variable distributions. In cross sectional analyses, results from each of the outcome measures (frataxin levels, platelet metabolic markers, ApoA-1, and recovery time from CrCEST) will

be used as dependent variables in multiple linear regression models or mixed models examining the independent effects of age, GAA repeat length and sex as dependent variables. This will allow us to define the degree to which each outcome marker is predicted by genetic severity (GAA repeat length), disease progression (age) or both. We will also directly correlate results between MEP and CrCEST to ascertain the degree to which they reflect the same construct (FRDA disease progression). Finally, we will examine correlations and regression modelling between physiological results and clinical measures (Aim 1) and frataxin levels (Aim 2)

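### MEP size, recorded at 110% of motor threshold, is the only MEP endpoint and largely omits threshold change; RMT, which would show it, has no planned analysis

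*Combined protocol and SAP*

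**What the plan says.** Section 4.5 (MEP Measurements) fixes the threshold by a response criterion: "Resting motor threshold (RMT) will be measured as the minimum stimulus intensity needed to elicit MEPs of at least 50uV in 5 of 10 trials". Searching for it belongs to the MEP procedure: "Finding the RMT and optimal site will take approximately 20-30 single stimuli". Recording follows, with 20 test stimuli given "at a pulse intensity of 110% MT". No fixed absolute intensity, recruitment curve or scaling to a maximal response is described.

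The synopsis (Study Measures) and Section 4.9 make MEP testing annual, in 30 children at CHOP.

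Section 4.7 gives the Aim 3 endpoints: "The primary endpoints are the post exercise recovery time, Tau, for CrCest and the MEP size for MEP testing". Their use is stated next: "The rate of change over time will be determined to define which measures are most sensitive to disease progression".

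In Section 4.8, the dependent variables of the cross-sectional Aim 3 models are listed in these words: "results from each of the outcome measures (frataxin levels, platelet metabolic markers, ApoA-1, and recovery time from CrCEST) will". That list names neither MEP size nor RMT. RMT appears only in Section 4.5, as a calibration step. It is not named as an outcome or a covariate in Section 4.7 or 4.8.

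**The concern.** Threshold is the intensity that produces a fixed small response, and the test pulse is a fixed multiple of that intensity. If a child's threshold rises between annual sessions and is measured again, the pulse rises too, and the response is again taken just above the 50 uV anchor. The threshold part of any loss of corticospinal excitability is then held in RMT, and the plan does nothing with RMT.

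Aim 3 asks how physiological dysfunction progresses and which measures follow it best. A flat MEP-size trend could be taken to mean that excitability did not change, or that MEP testing is insensitive, when the planned analysis never looked at the threshold component. Section 4.8 notes that MEP has separated patients from controls. That is a between-group result and does not show that an amplitude taken relative to threshold follows change within a child.

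**Working it through.** The documents give no effect size, SD, alpha or power for MEP, so there is no stated figure to reproduce. The check is whether the endpoint definition lets a threshold change through.

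**Inputs from the documents (Section 4.5).** Threshold criterion 50 uV = 0.05 mV; test intensity 1.10 x threshold.

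**Assumed inputs.** A sigmoid recruitment curve, with intensity I in % of maximum stimulator output:

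- MEP(I) = M / (1 + exp((S50 - I)/k))
- RMT = S50 - k x ln(M/0.05 - 1)
- M (maximal response) 2-5 mV, k (slope constant) 5-9, S50 (midpoint) 60 at baseline. None of these comes from the documents.

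**1. Curve shifts right, slope unchanged (S50 from 60 to 70).** Worked case k = 7, M = 3:

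- ln(3/0.05 - 1) = ln 59 = 4.078. RMT before = 60 - 7 x 4.078 = 31.5; after = 70 - 28.5 = 41.5.
- MEP at 110% of own RMT: 0.078 mV before (I = 34.6), 0.089 mV after (I = 45.6), a change of +15%.
- MEP at the baseline intensity (I = 34.6) on the shifted curve: 0.019 mV, a change of -76%.

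Over k = 5-9 and M = 2-5, RMT rises 10 points, MEP size at 110% RMT rises 11-22%, and MEP at the baseline intensity falls 66-86%.

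**2. Curve shifts right, slope constant grows in proportion.** Multiply S50 and k by the same factor c. RMT is multiplied by c, and (S50 - 1.1 x RMT)/k does not change, so MEP size at 110% RMT changes by exactly 0% for any c. With M = 2, S50 = 60, k = 5 (RMT 41.7), raising both by 10-20% raises RMT by 10-20%, and MEP at the baseline intensity falls 55-77%.

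**3. Maximal response falls, same baseline as step 2.** M down 25-50%: RMT rises 4-9%, MEP size at 110% RMT rises 2-3%, and MEP at the baseline intensity falls 25-50%.

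**4. Slope flattens at an unchanged threshold, same baseline.** k up 20-40%: MEP size falls 12-20% on either basis. The endpoint does register this change.

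**5. Ceiling.** 110% of RMT can be delivered only if RMT <= 100/1.1 = 90.9% of output. Section 4.5 gives no rule for a child above that.

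Steps 1 to 3 move RMT while MEP size stays level or rises modestly. Step 4 moves MEP size while RMT stays put. The two quantities carry different information, and only one of them has a planned analysis.

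**The case against.** **The result depends on the curve.** This stands in part. If S50 goes from 60 to 70 and k also rises 40%, MEP size at 110% RMT falls 10-18% over the same grid. But RMT then moves only -6.5 to +2.7 points, so this is mainly a slope change and does not answer the threshold point. A reader might infer that the endpoint cannot see loss of excitability at all. Step 4 shows that it can see a slope change, and the documents do not say which component Friedreich's ataxia alters.

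**The fixed-intensity comparison is not a practical rival.** This stands. In step 1 it leaves responses of 14-23 uV, below the protocol's own 50 uV criterion. It shows where the change goes and is not proposed as an endpoint. The 11-22% rise is only 7-23 uV, and the documents give no MEP variability to set it against.

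**The ceiling may never matter.** This stands. A reader might infer that the most affected children will drop out because of high thresholds. The documents give no RMT values, and in the assumed grid RMT runs from 19% to 52% of output, far below 90.9%.

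**Re-thresholding each year is not written down.** This is correct. Section 4.5 describes one procedure and writes MT after defining RMT. Still, the search is part of that procedure, and nothing suggests carrying a baseline intensity forward.

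**A flat MEP size would be a legitimate finding in a descriptive sub-study.** It would be, about that measure. It would not justify a statement about excitability in general. The phrase in Section 4.8 about physiological values from MEP could loosely cover RMT, but it does not name it.

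**Conclusion.** The point holds in a limited form. With the pulse tied to a threshold that is itself anchored at 50 uV, a change in threshold over time is largely removed from MEP size and goes into RMT, which has no planned analysis. Under the assumed sigmoid, a 10-point rise in RMT leaves MEP size unchanged (slope scaling in proportion) or 11-22% larger (slope fixed).

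This rests on two things that the documents do not supply: that threshold is redetermined at each annual session, and the shape of the recruitment curve. The percentages illustrate direction and rough size; they do not predict this cohort's results.

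Two stronger readings are not supported: that MEP size is insensitive to all loss of excitability, and that high-threshold children will in fact go missing. Stimulating relative to threshold is not itself at fault. The gap is doing so while leaving threshold out of the analysis. It biases no treatment comparison, but it weakens Aim 3's ability to answer its own question and can be closed with data that the procedure already generates.

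**What to change.** - In Section 4.7, add RMT (% of maximum stimulator output) from each annual MEP session as an Aim 3 outcome with its own rate of change. Analyse it by age, sex and GAA repeat length, as already planned for the other measures, and interpret MEP size jointly with it.
- In Section 4.5, state whether RMT is redetermined at every annual session, and use one term for RMT and MT.
- In Section 4.8, name both MEP size and RMT among the Aim 3 outcomes.
- State how the data are handled if 110% of RMT exceeds maximum output (RMT > 90.9%; frequency unknown). Keep the child's measured RMT in the analysis, and report MEP size as not obtainable because of high threshold. Treat RMT as right-censored only where no threshold can be found.

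**Cost.** No added stimuli, visits or procedures, since RMT must be found to set the pulse. There is one more outcome to record and report. The cohort is aged 2 to 18, and Section 4.9 uses controls only if needed, so an RMT slope may mix maturation with disease. Adjusting for age helps but cannot fully separate the two, and the report should say so.

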4.6 Abstracted Data Elements

Friedreich Ataxia Clinical Outcome Measures Study (CHOP IRB# 01-002609): Below are the listed data elements that will be abstracted from this study. This includes data collected before and during the participant's enrollment.

- Functional Staging for Ataxia Score
- Friedreich Ataxia Rating Scale (FARS)
- Medical History Update- FA Symptoms Review
- Medical History Update Medical Conditions Log
- Medical History Update Medications
- Vital Signs- height, weight, BMI, blood pressure
- 9 Hole Peg Test
- Timed 25 Foot Walk
- Extended Timed Walks
- Activities of Daily Living
- Pediatric Quality of Life Questionnaires

4.7 Primary and Secondary Endpoints

The primary goal of this study is to gather long-term serial quantitative clinical data using the measures validated during the three years of the study.

Aims 1: The primary endpoint (s) are the change in each of the clinical measures over time. The rate of change of each of these will be compared for responsiveness to change (SD of change/mean change).

Aim 2: Biochemical measures: The rate of change of frataxin and each platelet biomarker will be determined as primary endpoints. The rate of change over time will be determined to define which measures are most sensitive to disease progression.

Aim 3: Anatomical measures: The primary endpoints are the post exercise recovery time, Tau, for CrCest and the MEP size for MEP testing. The rate of change over time will be determined to define which measures are most sensitive to disease progression.

The secondary analyses are:

The rate of change of each measure the (neurological measures, biochemical measures and anatomic measures) as a function of age, GAA repeat length and sex, as determined by linear regression models

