2.1 Primary Objective (or Aim)

Aim 1: Identify markers of disease progression in children with FRDA and assess potential clinical measures of disease progression in the youngest subjects (n=110).

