3.1.2 Assessment Phase

Visit 1 (0 months) Subjects will be assessed by medical history, neurological tests (FARS, Timed 25 foot walk (T25W), Timed 1 and 6 minute walks, Timed up and go (TUG), Berg Balance scale (BBS), 9 hole peg test (9HPT), PedsQL, ADL score and ataxia disability scale), biochemical tests (frataxin level, platelet metabolic biomarkers), and physiological testing (CrCEST, MEP). Data will be collected over a one day visit.

Visit 2. (6 months) Subjects will be assessed by medical history, neurological tests (FARS, Timed 25 foot walk (T25W), Timed 1 and 6 minute walks, TUG, BBS, 9HPT, PedsQL, ADL score, ataxia disability scale), and biochemical tests (frataxin level, platelet metabolic biomarkers). Data will be collected over a one day visit.

Visit 3 (12 months) Subjects will be assessed by medical history, neurological tests (FARS, Timed 25 foot walk (T25W), Timed 1 and 6 minute walks, Timed up and go (TUG), Berg Balance scale (BBS), 9 hole peg test (9HPT), PedsQL, ADL score and ataxia disability scale), biochemical tests (frataxin level, platelet metabolic biomarkers), and physiological testing (CrCEST, MEP). Data will be collected over a one day visit.

Visit 4. (18 months) Subjects will be assessed by medical history, neurological tests (FARS, Timed 25 foot walk (T25W), Timed 1 and 6 minute walks, TUG, BBS, 9HPT, PedsQL, ADL score, ataxia disability scale), and biochemical tests (frataxin level, platelet metabolic biomarkers). Data will be collected over a one day visit.

Visit 5 (24 months) Subjects will be assessed by medical history, neurological tests (FARS, Timed 25 foot walk (T25W), Timed 1 and 6 minute walks, Timed up and go (TUG), Berg Balance scale (BBS), 9 hole peg test (9HPT), PedsQL, ADL score and ataxia disability scale), biochemical tests (frataxin level, platelet metabolic biomarkers), and physiological testing (CrCEST, MEP). Data will be collected over a one day visit.

Visit 6 (36 months) Subjects will be assessed by medical history, neurological tests (FARS, Timed 25 foot walk (T25W), Timed 1 and 6 minute walks, Timed up and go (TUG), Berg Balance scale (BBS), 9 hole peg test (9HPT), PedsQL, ADL score and ataxia disability scale), biochemical tests (frataxin level, platelet metabolic biomarkers), and physiological testing (CrCEST, MEP). Data will be collected over a one day visit.

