3.3.2 Total Number of Study Sites/Total Number of Subjects Projected

The study will be conducted at 3 investigative sites in the United States. Clinical neurological (Aim 1) assessments and frataxin sample collections (Aim 2) will be carried out at all three sites. Physiological assessments (Aim 3) will only be conducted at CHOP.

The following is a list of sites included in the study:

Children's Hospital of Philadelphia

University of California Los Angeles

University of Florida

The University of Rochester will provide database support

Recruitment will stop when 110 children are enrolled (up to 90 at CHOP, up to 20 at other sites). The majority of subjects will be enrolled at the CHOP site and some will be included to participate in the MEP (n=30) and CrCEST (n=12) measures. A substantial number of participants will be recruited from the ongoing natural history study of all ages, FACOMS, in which some children are already enrolled. [name] sees 30 new FRDA patients per year, with the majority being children. Study advertisements will be sent through the Friedreich Ataxia Research Alliance (FARA) registry, which is a database that includes 141 children living in the United States and over 2000 patients worldwide.

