3.4 Study Population

3.4.1 Inclusion Criteria

1) Males or females age 2 to 18 years.

- Genetically confirmed diagnosis of FRDA or clinically confirmed diagnosis of FRDA, pending confirmatory genetic testing through a commercial or research laboratory
- 3) Parental/guardian permission (informed consent) and if appropriate, child assent.
- 4) Weight \geq 10 kg (for the MEP measures only)

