- g) The Pediatric Quality of Life (PedsQL) and the FARS ADL scores. Subjects aged 2-7 inclusive will not need to complete a PedsQL scale. The PedsQL scale is the Pediatric Quality of Life Inventory. This scale has two separate questionnaires: one is designed for subjects between the ages of 8-12, the other for subjects between 13-18. The subject will answer the questionnaire with the help of the study coordinator. The subject's parent or guardian will also answer a separate questionnaire on the same topic. The FARS ADL score is a similar questionnaire asking the participant how they view their performance on tasks such as dressing, bathing, etc. Subjects and their guardians will be asked to complete questionnaires annually.

In some situations, such as a global pandemic, travel restrictions, as well as poor health or an overall concern for safety, it may not be possible for subjects to have an in-person visit every year. Under these circumstances, for subjects who have previously consented for this study it is possible to conduct a visit remotely via phone or video/telehealth. A remote visit will not include the 9HPT or any sample collection. Remote visits can include the following: review of consent forms, medical history and medications, completion of questionnaires that can be mailed or emailed to subjects, certain assessments of gait and motor functioning including answers to the surveys which ask questions about gait and motor abilities, parts of the FARS exam (for example, the Bulbar facial nerve function exam which can be performed and viewed over video), and timed standing and/or walking tests that can be viewed over video (provided that it has been determined ahead of time to be a low fall risk to the subject - fall risk will be determined by taking a recent detailed fall history of each subject prior to any standing or walking test).

All procedures detailed above (except the BBS and TUG) have been included on other IRB approved studies at CHOP, including a currently open study (IRB 01-002609).

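### Section 4.7 compares Aim 1 measures by SD of change/mean change, but the measures are not obtained in the same children and no matched sample is specified.

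*Combined protocol and SAP*

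**What the plan says.** Section 4.7 makes change over time in each clinical measure the Aim 1 primary endpoint and then ranks the measures: "The rate of change of each of these will be compared for responsiveness to change (SD of change/mean change". On this scale a smaller value means a more responsive measure. The comparison is not tied to any age band or common set of children.

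Four other places bear on who contributes to each ratio.

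- Section 3.4.1 sets eligibility as "Males or females age 2 to 18 years".
- Section 4.1 says "Subjects aged 2-7 inclusive will not need to complete a PedsQL scale". Of the two PedsQL forms, "one is designed for subjects between the ages of 8-12, the other for subjects between 13-18".
- Section 5.6 does not ask children who are non-ambulatory, more severely affected or have cardiomyopathy to do the timed walks.
- Section 4.7 (secondary analyses) regresses rate of change on age, GAA repeat length and sex, and section 4.8 models each Aim 1 test accounting for the same variables.

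On population, section 2.1 aims to "assess potential clinical measures of disease progression in the youngest subjects (n=110" in number, and section 3.3.2 says "Recruitment will stop when 110 children are enrolled".

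**The concern.** A responsiveness ratio belongs to a measure in a particular group of children over a particular interval. If one measure is scored on a group that progresses faster or varies less, its ratio improves even when the two measures would perform alike in the same children.

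Section 4.7 invites readers to rank the measures by this ratio, and the study's stated purpose is to find measures usable in later pediatric trials. A ranking that partly reflects who was tested could lead to the wrong choice. PedsQL differs from the other measures by age, and the timed walks differ by severity and cardiac status.

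**Working it through.** **The plan's own figure.** Section 3.3.2 allows up to 90 children at the main site and up to 20 at the other two: 90 + 20 = 110. This agrees with the n in Aim 1. Section 4.9 gives no alpha, power, effect size or SD, so nothing further can be reproduced.

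**Who contributes to each ratio.**

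| Measure | Children covered | Source |
|---|---|---|
| PedsQL | Required from age 8 | 4.1 |
| Timed walks | Not the non-ambulatory, the more severely affected or those with cardiomyopathy | 5.6 |
| Other Aim 1 measures | No comparable restriction by age or severity found | 3.4.1, 4.1 |

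No section limits the 4.7 comparison to children or visits that have both measures.

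**Can coverage alone move the ratio?** All inputs here are assumptions. The SD of change is 1 within each age band. The share aged 2-7 is y = 10%, 20% or 6/17 (about 35%, which is uniform ages over 2-18). The rest is split 5:6 between ages 8-12 and 13-18. For band weights w, means m and SDs s:

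μ = Σ w·m; variance = Σ w(s² + m²) − μ²; ratio = √variance / |μ|.

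Worked case, mean changes 0 / −0.3 / −0.6 in the three bands:

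- Ages 8-18 only: μ = (5 × −0.3 + 6 × −0.6)/11 = −0.464. Mean square = (5 × 0.09 + 6 × 0.36)/11 = 0.2373. Variance = 1 + 0.2373 − 0.2150 = 1.0223. Ratio = 1.011/0.464 = 2.18.
- Ages 2-18, y = 10%: μ = 0.9 × −0.4636 = −0.417. Variance = 1 + 0.9 × 0.2373 − 0.1741 = 1.0394. Ratio = 1.020/0.417 = 2.44.

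| Assumed mean change at 2-7 / 8-12 / 13-18 | 8-18 only | 2-18, y = 10% / 20% / 35% |
|---|---|---|
| −0.25 / −0.25 / −0.25 | 4.00 | 4.00 / 4.00 / 4.00 |
| −0.2 / −0.3 / −0.4 | 2.82 | 2.96 / 3.10 / 3.35 |
| 0 / −0.3 / −0.6 | 2.18 | 2.44 / 2.77 / 3.44 |
| −0.6 / −0.3 / 0 | 7.41 | 5.58 / 4.48 / 3.44 |

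In every row the measure behaves identically at each age; only the children covered change. The shift is nil, favourable or adverse depending on a pattern the documents do not give. The table gives entrants aged 2-7 no weight in the 8-18 column. Children who turn 8 during follow-up would contribute some PedsQL change over a shorter span, and this is not modelled. The same formula applies to the timed walks, with the share not asked to walk in place of the share aged 2-7.

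**Why a supplement by age is useful.** Take the third pattern against a measure with mean change −0.25 at all ages (ratio 4.00). At y = 0.443 the third pattern has μ = 0.557 × −0.4636 = −0.258, variance = 1 + 0.557 × 0.2373 − 0.0667 = 1.0655 and ratio = 1.032/0.258 = 4.00. Below about 44% aged 2-7 it is therefore ranked ahead, although it has no mean change at ages 2-7.

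**Precision.** With r = mean/SD, SE(r) = √(1/n + r²/(2n)), and the 95% limits are inverted to SD/mean. At an assumed true ratio of 2.0 (r = 0.5):

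| n | 95% interval for SD/mean |
|---|---|
| 110 | 1.43 to 3.31 |
| 99 | 1.41 to 3.44 |
| 71 | 1.34 to 3.95 |
| 39 | 1.20 to 5.98 |
| 22 | 1.06 to 17.6 |
| 11 | upper limit unbounded |

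Here 99 and 71 are what remains of 110 if 10% or 35% are aged 2-7; 11, 22 and 39 are 10%, 20% and 35% of 110. Dropout is ignored.

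**The case against.** The strongest reply is that age is already handled: 4.7 regresses each rate of change on age, and 4.8 models each test with age. That stands as far as it goes, and a reader should not infer that the plan ignores age. With a linear age effect and constant SD, the fitted mean and residual SD could even approximate responsiveness by age. But the plan does not commit to reporting that, and neither model puts two measures' ratios on the same children.

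A second reply is that only PedsQL is restricted by age, and that it may not be a clinical measure for 4.7, because the synopsis lists quality of life separately. Sections 3.1.2 and 4.1 place it among the neurological measures, so its inclusion is arguable. The age mismatch does concern PedsQL alone; the walk restriction is by severity and cardiac status. If PedsQL is left out, the walk mismatch remains.

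Third, the effect is hypothetical. That is correct, and no bias of known direction should be claimed.

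Two stronger readings are tempting and not supported.

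- A reader might work out exact PedsQL spans: no change score for entry at 2-5, and 36 months for every entry at 8 or over. This depends on the schedule. Section 3.1.2 passes from 24 months to "Visit 6 (36 months) Subjects will be assessed by medical history", with no 30-month visit, whereas 4.9 has clinical tests every six months through 36 months. With a 30-month visit, a child entering at 5.5 or older would have two PedsQL visits. At the upper end the forms stop at 18, and handling after that age is not stated. The text for ages 2-7 is also an exemption, not a bar.
- A reader might infer that Aim 1 promises an analysis of a younger subgroup that 4.7 omits. The n of 110 is the whole cohort, and recruitment draws on an "ongoing natural history study of all ages, FACOMS, in which some children are already enrolled". Reading youngest as all enrolled children fits the text.

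**Conclusion.** The point holds for the between-measure comparison in 4.7. As written, a difference in SD of change/mean change can reflect who was assessed and over what span, and the age regressions do not correct this. That conclusion rests on sections 4.1, 4.7 and 5.6 and needs no assumed numbers.

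The size is not known. The illustrated shifts run from none (4.00 against 4.00) to large in either direction (2.18 against 3.44; 7.41 against 3.44), all under assumed age shares, mean changes and a common SD. The pooled ratio for a single measure is not invalid; it needs its n and its population stated. The wording of the youngest subjects in 2.1 is a minor clarification.

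**What to change.** In 4.7, keep the pooled ratio for each measure and report its n. Add that any comparison between two measures uses only children and visits where both were obtained, over the same interval: PedsQL against other measures at ages (at assessment) where both are collected, and timed walks against other measures in children who performed both.

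As a descriptive supplement, report n, mean change, SD of change and the ratio with an interval by pre-specified age-at-entry band, for example 2-7, 8-12 and 13-18, and state that this is not a firm ranking. Show mean and SD beside the ratio, because it is unbounded as mean change nears zero. In 2.1, add a phrase saying whether youngest means all enrolled children.

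The cost is wording and tables on data already collected. Matched comparisons lose children: at an assumed ratio of 2.0, going from 110 to 71 widens the interval from 1.43-3.31 to 1.34-3.95. Band intervals may be very wide (1.06-17.6 at n = 22) or unbounded (n = 11), which is why they should remain descriptive.
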